11.5 Clinical Laboratory Tests (Serum Chemistry, Hematology, Urinalysis)

Clinical laboratory tests will be performed at Screening and end-of-study.

Clinical laboratory test results will be summarized overall by time point and listed by subject.

Out-of-range values and corresponding recheck results will be listed.

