5.6 End-of-Study (End of Week 6 Visit or on Early Discontinuation)

At the end of the study, the following procedures will be performed:

- Review of AEs and concomitant medication use.
- Vital signs
- Body weight
- 12-lead ECG
- Clinical chemistry, hematology and urinalysis
- Symptom-driven physical examination, if applicable
- Provide smoking cessation information

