6.3 Data Analysis and Summarization

SAS software (version 9.3 or higher, Cary, North Carolina) will be used for all data presentation and summarization including statistical analyses, summary tables, graphs, and data listings. In general, all data will be listed by subject and time point and summarized by group and time point using descriptive statistics appropriate for the endpoint. Absolute and percent change from baseline values will also be listed and summarized where appropriate. Figures will be used to display the data graphically.

Missing data will not be imputed. Where individual data points are missing because of dropouts or other reasons, the data will be considered missing at random and summarized based on reduced denominators.

Within-group comparisons will be made for all groups for endpoints that have baseline (end of Week -1) and post-baseline measurements.

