11.6 Vital Signs

Vital signs (respiratory rate, pulse rate, blood pressure, and oral temperature) will be measured in the sitting position at Screening, at each study visit (weeks -1, 2, 4) and at the end-of-study (Week 6).

Vital signs will be listed by subject and time point of collection and be summarized by product group and time point.

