11.7 Electrocardiogram

Electrocardiogram will be performed at Screening and listed by subject.

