12. SUMMARY OF CHANGES FROM PROTOCOL-PLANNED ANALYSIS

The analyses described in this SAP are aligned with those analyses described in the protocol.

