UB mentholated = Subjects' UB mentholated filtered cigarettes

Program: /CAXXXX/sas_prg/stsas/lis_PROGRAMNAME.sas DDMMYYYY HH:MM

Programmer Notes: Replace Parameter1, 2 etc. with actual lab tests in the study. Sort unscheduled assessment and early termination chronologically with other scheduled assessments and rechecks. Recheck should be sorted with the scheduled time point the recheck is for.

Programmer Notes: Clinically significant lab values generally will be captured as AEs, some of which the PI may indicate in Appendix 16.2.8.1.5 lab comments (as per GPG.03.0028 sections 2.9 and 2.10). Derive an additional CS flag for PI flag (+) based on positive comments (i.e. CS/Clinically Significant). Present this derived 4th column in all tables, and list only subjects/tests which are PI-determined clinically significant lab values in Table 14.3.4.4.

Program: /CAXXXX/sas_prg/stsas/tab_PROGRAMNAME.sas DDMMYYYY HH:MM

Post-text Table 14.3.4.4 will be in the following format:

Page 1 of X

Table 14.3.4.4 Clinically Significant Laboratory and Corresponding Results (Safety Population)

Subject Number	Age/ Sex	Visit		Product Group	Date	Time	Department	Test	Result	Reference Range	Unit
		Name	Date								
XXXXXX	XX/X	Screening	DDMMYYYY	XX	02DEC2016	8:34	Serum Chemistry	Cholesterol	XXX	X - X	mg/dL

Programmer Note: All time points for a subject/test with at least one value deemed as CS by the PI will be presented in this table.

Note: F = Female, M = Male
H = Above Reference Range, L = Below Reference Range
N = Not Clinically Significant

VLN non-mentholated = Non-mentholated VLN cigarettes
VLN mentholated = Mentholated VLN cigarettes
UB non-mentholated = Subjects' UB non-mentholated filtered cigarettes
UB mentholated = Subjects' UB mentholated filtered cigarettes

Program: /CAXXXX/sas_prg/stsas/lis_PROGRAMNAME.sas DDMMYYYY HH:MM

If no event meet this criteria then include a statement as follows:

"There were no clinical laboratory results documented as clinically significant by the PI."

Page 1 of X

Post-text Tables 14.3.5.1, 14.3.5.2, and 14.3.5.3 will be in the following format:

Page 1 of X

Table 14.3.5.1 Clinical Laboratory Summary - Serum Chemistry (Safety Population)

Laboratory Test (unit)	Reference Range	Statistics	Time Point	
			Screening	End of Study
XXXXXXXXXX	XX -XX	n	X	X
		Mean	X.X	X.X
		SD	X.XX	X.XX
		Minimum	XX	XX
		Median	X.X	X.X
		Maximum	XX	XX
XXXXXXXXXX	XX -XX#	n	X	X
		Mean	X.X	X.X
		SD	X.XX	X.XX
		Minimum	XX	XX
		Median	X.X	X.X

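### The planned laboratory summary tables (SAP 11.5, Tables 14.3.5.1 to 14.3.5.3) pool all four product groups, so they cannot separate a VLN shift from drift common to both arms

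*SAP*

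**What the plan says.** **Timing.** SAP 11.5 says "Clinical laboratory tests will be performed at Screening and end-of-study". Protocol 5.6 agrees, listing "Clinical chemistry, hematology and urinalysis" among the procedures at the end of Week 6 or on early discontinuation. End of study is thus the one scheduled safety panel after the switch.

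**Level of summary.** SAP 11.5 continues: "Clinical laboratory test results will be summarized overall by time point and listed by subject". In SAP 14.3, the shell that begins "Table 14.3.5.1 Clinical Laboratory Summary - Serum Chemistry (Safety Population" also serves hematology and urinalysis. Beside the labels for test, reference range and statistic it has two data columns, Screening and End of Study. It has no product group and no change from Screening.

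**Other safety data.** SAP 11.6 says vital signs will "be summarized by product group and time point", and the shell of Table 14.3.5.4 has four product-group columns. The AE frequency tables (12-1, 14.3.1.1 and 14.3.1.2) also have a column for each group.

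**The protocol.** Section 6.3 states, as a general rule, that "all data will be listed by subject and time point and summarized by group and time point". The synopsis leaves laboratory summary statistics optional, and Section 6.4 omits laboratory tests from the safety items to be summarised. SAP 12 says: "The analyses described in this SAP are aligned with those analyses described in the protocol".

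**The concern.** The trial has concurrent usual-brand groups that undergo the same end-of-study panel as the VLN groups. A before-and-after table that pools the two makes no use of them.

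Common drift is plausible here. Screening can fall up to 28 days before Week -1, and participation then lasts 7 weeks, so the two panels can be 28 + 49 = 77 days apart. Subjects are also selected partly on their Screening laboratory results (Protocol 3.2, criterion 2), which invites regression toward the mean in every group.

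What is at stake is how the laboratory safety data can be read. A reader of the three summary tables would see one change and could not tell whether it came from VLN, from time and selection, or from both.

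**Working it through.** The documents give no sample size, SD or threshold for laboratory tests, so there is no planned figure to reproduce. The check asks what the pooled table can show.

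**Inputs**
- Planned allocation (Protocol 2.1, SAP 3): VLN 50 + 50 = 100; usual brand 20 + 20 = 40; total 140.
- Analysis set: the SAP 5 safety population takes enrolled subjects who smoked any type of cigarette, so the usual-brand continuers are in these tables.
- Assumption: every subject has both panels.

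**Pooled mean change**

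Pooled change = (100/140) × VLN change + (40/140) × UB change = 0.714 × VLN change + 0.286 × UB change.

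| VLN change | UB change | VLN minus UB | Pooled table shows |
|---|---|---|---|
| 1.00 | 0 | 1.00 | 0.714 |
| 0.714 | 0.714 | 0 | 0.714 |
| 0.80 | 0.30 | 0.50 | 0.657 |

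The first two rows give the same table, although the VLN effect is 1.00 in one and nil in the other. The first row also gives the dilution: 1 − 0.714 = 0.286, or 29%.

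**Pooled proportions** (illustrative rates for an abnormal result)
- 10% on VLN and 2% on UB: (100 × 0.10 + 40 × 0.02)/140 = 7.7%.
- 5% on VLN and 14.5% on UB: (100 × 0.05 + 40 × 0.145)/140 = 7.7%.

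Opposite differences between the arms give the same pooled rate.

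**Would a table by group be informative?** In units of the SD of the change, with a normal approximation and no dropout:
- VLN combined against UB combined: SE = √(1/100 + 1/40) = 0.187. The 95% CI half-width is 1.96 × 0.187 = 0.37 SD. The difference detectable with 80% power at two-sided 0.05 is (1.960 + 0.842) × 0.187 = 0.52 SD.
- Within one flavour (50 against 20): SE = √(1/50 + 1/20) = 0.265, half-width 0.52 SD, detectable difference 0.74 SD.

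The planned numbers therefore support a useful descriptive comparison, best for the combined groups.

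**The case against.** **The data are not lost.** A reader might infer that the post-switch laboratory data cannot show a VLN effect at all. The documents do not support that. The shells for the out-of-range tables (14.3.4.1 to 14.3.4.3), the clinically significant table (14.3.4.4) and the listings (Appendices 16.2.8.1.1 to 16.2.8.1.3) all carry product group. A programmer note in SAP 14.3 adds that clinically significant values will generally be recorded as AEs, which are tabulated by group. This stands, and it limits the point to the summary tables. Those displays still do not fill the gap: the laboratory ones are by subject, give no group means or denominators, and the out-of-range tables miss shifts inside the reference range.

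**The protocol conflict is weak.** A reader might also infer that the SAP breaches the protocol and that the alignment statement in SAP 12 is false. That goes too far. The Protocol 6.3 rule is only general, the synopsis makes laboratory summaries optional, and Section 6.4 names vital signs but not laboratory tests. What remains is an inconsistency with the general rule and with the SAP's own handling of vital signs.

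**The stakes are low.** AEs are the only named safety endpoint (Protocol 2.2, SAP 2.4), and no hypothesis or power statement concerns laboratory values. The 0.71 is the allocation ratio applied to a hypothetical shift; it does not show that any decision would change. All of this stands.

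**Causal wording needs care.** Protocol 2.1 calls the study non-randomized while SAP 3 calls it randomized, and the topography and PK subjects are tied to VLN. The usual-brand groups are therefore best described as concurrent controls.

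**ECG.** SAP 11.7 says "Electrocardiogram will be performed at Screening and listed by subject", while Protocol 5.6 also schedules a 12-lead ECG at end of study. A reader might infer that the second ECG goes unreported. SAP 11 lists all CRF data chronologically, and the shell of Appendix 16.2.8.3 has visit, time point and product group, so it would be listed. No ECG summary is required; only the sentence is incomplete.

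**Conclusion.** The point holds for the three laboratory summary tables. SAP text and shell agree that they pool the groups. At planned sizes and with complete panels, a VLN-only shift shows at 0.71 of its size, and common drift cannot be told apart from a product effect. The weight is modest. What is missing is a laboratory summary at group level. Product group is available in the by-subject and AE displays, and no primary or secondary endpoint changes. The change is worth making because it is almost free and uses concurrent control data that the trial already collects.

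**What to change.** - **SAP 11.5:** change the sentence to say that results are *summarized by product group and overall, by time point*.
- **Shell for Tables 14.3.5.1 to 14.3.5.3:** add columns for the four product groups, VLN combined, UB combined and overall. Add change from Screening for continuous tests. For qualitative urinalysis items such as nitrite or ketones, where a mean change does not apply, give frequency counts by group and time point.
- **SAP 11.7:** at most, mention the end-of-study ECG that Protocol 5.6 schedules. No ECG summary table is needed.

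The cost is a sentence or two of SAP text and one table shell used three times. No new assessment, sample or data field is needed, because product group is already attached to each laboratory record in the listings.

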11.6 Vital Signs

Vital signs (respiratory rate, pulse rate, blood pressure, and oral temperature) will be measured in the sitting position at Screening, at each study visit (weeks -1, 2, 4) and at the end-of-study (Week 6).

Vital signs will be listed by subject and time point of collection and be summarized by product group and time point.

11.7 Electrocardiogram

Electrocardiogram will be performed at Screening and listed by subject.

11.8 Concomitant Medications

All concomitant medications recorded during the study will be coded with the WHO Dictionary Version 01SEP2018 and listed.

11.9 Physical Examination

Physical examinations will be performed at Screening. Symptom-driven physical examination may be performed at Week -1, end-of-study (Week 6) and follow-up. All data found in the CRF will be listed. Changes in physical examinations (if any) will be described in the text of the final report.

12. SUMMARY OF CHANGES FROM PROTOCOL-PLANNED ANALYSIS

The analyses described in this SAP are aligned with those analyses described in the protocol.

13. SUMMARY TABLES AND FIGURES

Summary tables and figures are numbered following the International Conference on Harmonization (ICH) structure but may be renumbered as appropriate during the compilation of the tables and figures for the CSR. Note that all summary tables and figures will be generated using SAS[®] Version 9.3.

13.1 In-text Summary Tables and Figures

The following is a list of table and figure titles that will be included in the text of the CSR. Tables and figures will be numbered appropriately during compilation of the CSR.

Section 10:

Table 10-1 Subject Disposition Summary (Safety and PP population)

Section 11:

Table 11-1 Demographic and Smoking History Summary (Safety and PP population)

Table 11-2 Summary of Number of Cigarettes Smoked per Week by Study Product Group and Study Week (PP Population)

Table 11-3 Statistical Comparison of Number of Cigarettes Smoked per Week at Weeks 2 and 6 Versus Week -1 by Study Product Group (PP Population)

Table 11-4 Summary of Puffing Topography Parameters by Study Product Group and Study Week (PP Population)

Table 11-5 Statistical Comparison of Puffing Topography Parameters at Weeks 2 and 6 Versus Week -1 by Study Product Group (PP Population)

Table 11-6 Summary of Urinary NNAL Mass Excreted (unit) by Study Product Group and Study Week (PP Population)

Table 11-7 Statistical Comparison of Urinary NNAL Mass Excreted (unit) at Weeks 2 and 6 Versus Week -1 by Study Product Group (PP Population)

Table 11-8 Summary of Urinary NNN Mass Excreted (unit) by Study Product Group and Study Week (PP Population)

Table 11-9 Statistical Comparison of Urinary NNN Mass Excreted (unit) at Weeks 2 and 6 Versus Week -1 by Study Product Group (PP Population)

Table 11-10 Summary of Urinary 3-HPMA Mass Excreted (unit) by Study Product Group and Study Week (PP Population)

Table 11-11 Statistical Comparison of Urinary 3-HPMA Mass Excreted (unit) at Weeks 2 and 6 Versus Week -1 by Study Product Group (PP Population)

Table 11-12 Summary of Urinary S-PMA Mass Excreted (unit) by Study Product Group and Study Week (PP Population)

Table 11-13 Statistical Comparison of Urinary S-PMA Mass Excreted (unit) at Weeks 2 and 6 Versus Week -1 by Study Product Group (PP Population)

Table 11-14 Summary of Urinary 1-OHP Mass Excreted (unit) by Study Product Group and Study Week (PP Population)

Table 11-15 Statistical Comparison of Urinary 1-OHP Mass Excreted (unit) at Weeks 2 and 6 Versus Week -1 by Study Product Group (PP Population)

Table 11-16 Summary of Urinary Tneq Mass Excreted (unit) by Study Product Group and Study Week (PP Population)

Table 11-17 Statistical Comparison of Urinary Tneq Mass Excreted (unit) at Weeks 2 and 6 Versus Week -1 by Study Product Group (PP Population)

Table 11-18 Summary of Blood COHb (unit) by Study Product Group and Study Week (PP Population)

Table 11-19 Statistical Comparison of Blood COHb (unit) at Weeks 2 and 6 Versus Week -1 by Study Product Group (PP Population)

Table 11-20 Summary of Baseline Adjusted Plasma Nicotine Pharmacokinetic Parameters Prior to and Following Use of VLN Cigarettes (Pharmacokinetic Population from PP)

Table 11-21 Statistical Comparison of Baseline Adjusted Plasma Nicotine Pharmacokinetic Parameters at Weeks 2 and 6 Versus Week -1 (Pharmacokinetic Population from PP)

Table 11-22 Summary of FTCD Score by Study Product Group and Study Week (PP Population)

Table 11-23 Statistical Comparison of FTCD Score at Weeks 2 and 6 Versus Week -1 by Study Product Group (PP Population)

Table 11-24 Summary of QSU-Brief Factor Score by Study Product Group and Study Week (PP Population)

Table 11-25 Statistical Comparison of QSU-Brief Factor Score at Weeks 2 and 6 Versus Week -1 by Study Product Group (PP Population)

Table 11-26 Summary of MNWS-R Total Score by Study Product Group and Study Week (PP Population)

Table 11-27 Statistical Comparison of MNWS-R Total Score at Weeks 2 and 6 Versus Week -1 by Study Product Group (PP Population)

Table 11-28 Summary of Perceived Health Risk Scale by Study Product Group and Study Week (PP Population)

Table 11-29 Statistical Comparison of Perceived Health Risk Scale at Weeks 2 and 6 Versus Week -1 by Study Product Group (PP Population)

Figure 11-1 Arithmetic Mean Number of Cigarettes Smoked per Week by Study Product Group and Study Week at Weeks -1, 2, and 6 (PP Population)

Figure 11-2 Arithmetic Mean Puffing Topography Parameter (Puff Duration) by Study Product Group and Study Week (PP Population)

Figure 11-3 Arithmetic Mean Puffing Topography Parameter (Puff Volume) by Study Product Group and Study Week (PP Population)

Figure 11-4 Arithmetic Mean Puffing Topography Parameter (Peak Puff Flow Rate) by Study Product Group and Study Week (PP Population)

Figure 11-5 Arithmetic Mean Puffing Topography Parameter (Average Flow Rate) by Study Product Group and Study Week (PP Population)

Figure 11-6 Arithmetic Mean Puffing Topography Parameter (Inter-puff Interval) by Study Product Group and Study Week (PP Population)

Figure 11-7 Arithmetic Mean Urinary NNAL Mass Excreted (unit) by Study Product Group and Study Week (PP Population)

Figure 11-8 Arithmetic Mean Urinary NNN Mass Excreted (unit) by Study Product Group and Study Week (PP Population)

Figure 11-9 Arithmetic Mean Urinary 3-HPMA Mass Excreted (unit) by Study Product Group and Study Week (PP Population)

Figure 11-10 Arithmetic Mean Urinary S-PMA Mass Excreted (unit) by Study Product Group and Study Week (PP Population)

Figure 11-11 Arithmetic Mean Urinary 1-OHP Mass Excreted (unit) by Study Product Group and Study Week (PP Population)

Figure 11-12 Arithmetic Mean Urinary Tneq Mass Excreted (unit) by Study Product Group and Study Week (PP Population)

Figure 11-13 Arithmetic Mean Blood COHb (unit) by Study Product Group and Study Week (PP Population)

Figure 11-14 Arithmetic Mean Unadjusted Plasma Nicotine Concentration-Time Profiles Following Following Use of UB (Week -1) and VLN Cigarettes (Weeks 2 and 6) (Pharmacokinetic Population from PP)

Figure 11-15 Arithmetic Mean Baseline-Adjusted Plasma Nicotine Concentration-Time Profiles Following Use of UB (Week -1) and VLN Cigarettes (Weeks 2 and 6) (Pharmacokinetic Population from PP)

Section 12:

Table 12-1 Adverse Event Frequency - Number of Subjects Reporting the Event (% of Subjects Used Product) (Safety Population)

13.2 Section 14 Summary Tables and Figures

The following is a list of table and figure titles that will be included in Section 14 of the report. Table and figure titles may be renumbered as appropriate during the compilation of the report.

14.1 Demographic Data Summary Tables

Table 14.1.1 Summary of Disposition (Safety and PP Populations)

Table 14.1.2 Demographic Summary (Safety and PP Populations)

Table 14.1.3 Tobacco/Nicotine Product Use History Summary (Safety and PP Populations)

14.2 Pharmacokinetic and Pharmacodynamic Data Summary Tables and Figures

14.2.1 Product Use Tables

Table 14.2.1.1.1.1 Summary of Number of Cigarettes Smoked per Week by Study Product Group and Study Week (PP Population)

Table 14.2.1.1.1.2 Summary of Number of Cigarettes Smoked per Week by Study Product Group and Study Week (ITT Population)

Table 14.2.1.1.2 Statistical Comparison of Number of Cigarettes Smoked per Week at Weeks 2 and 6 Versus Week -1 by Study Product Group (PP Population)

Table 14.2.1.1.3 Statistical Comparison of Number of Cigarettes Smoked per Week Among Study Product Groups at Weeks 2 and 6 (PP Population)

Table 14.2.1.2.1.1 Summary of Number of Cigarette Butts Collected per Week by Study Product Group and Study Week (PP Population)

Table 14.2.1.2.1.2 Summary of Number of Cigarette Butts Collected per Week by Study Product Group and Study Week (ITT Population)

Table 14.2.1.2.2 Statistical Comparison of Number of Cigarette Butts Collected per Week at Weeks 2 and 6 Versus Week -1 by Study Product Group (PP Population)

Table 14.2.1.2.3 Statistical Comparison of Number of Cigarette Butts Collected per Week Among Study Product Groups at Weeks 2 and 6 (PP Population)

14.2.2 Product Use Figures

Figure 14.2.2.1.1 Mean (\pm SD) of Number of Cigarettes Smoked per Week by Study Product Group and Study Week (PP Population)

Figure 14.2.2.1.2 Mean Number of Cigarettes Smoked per Week by Study Product Group and Study Week at Weeks -1, 2, and 6 (PP Population)

Figure 14.2.2.2.1 Mean (\pm SD) of Number of Cigarette Butts Collected per Week by Study Product Group and Study Week (PP Population)

Figure 14.2.2.2.2 Mean Number of Cigarette Butts Collected per Week by Study Product Group and Study Week at Weeks -1, 2, and 6 (PP Population)

14.2.3 Puff Topography Parameter Tables

Table 14.2.3.1.1 Summary of Puff Topography Parameters by Study Product Group and Study Week (PP Population)

Table 14.2.3.1.2 Summary of Puff Topography Parameters by Study Product Group and Study Week (ITT Population)

Table 14.2.3.2 Statistical Comparison of Puff Topography Parameters at Weeks 2 and 6 Versus Week -1 by Study Product Group (PP Population)

Table 14.2.3.3 Statistical Comparison of Puff Topography Parameters Among Study Product Groups at Weeks 2 and 6 (PP Population)

14.2.4 Puff Topography Parameter Figures

Figure 14.2.4.1 Mean Puffing Topography Parameter (Puff Duration) by Study Product Group and Study Week (PP Population)

Figure 14.2.4.2 Mean Puffing Topography Parameter (Puff Volume) by Study Product Group and Study Week (PP Population)

Figure 14.2.4.3 Mean Puffing Topography Parameter (Peak Puff Flow Rate) by Study Product Group and Study Week (PP Population)

Figure 14.2.4.4 Mean Puffing Topography Parameter (Average Flow Rate) by Study Product Group and Study Week (PP Population)

Figure 14.2.4.5 Mean Puffing Topography Parameter (Inter-puff Interval) by Study Product Group and Study Week (PP Population)

14.2.5 Biomarker Tables

Urine NNAL

Table 14.2.5.1.1.1.1 Summary of Urinary NNAL Mass Excreted (unit) by Study Product Group and Study Week (PP Population)

Table 14.2.5.1.1.1.2 Summary of Urinary NNAL Mass Excreted (unit) by Study Product Group and Study Week (ITT Population)

Table 14.2.5.1.1.2.1 Summary of Urinary NNAL Mass Excreted Change from Baseline (unit) by Study Product Group and Study Week (PP Population)

Table 14.2.5.1.1.2.2 Summary of Urinary NNAL Mass Excreted Change from Baseline (unit) by Study Product Group and Study Week (ITT Population)

Table 14.2.5.1.1.3.1 Summary of Urinary NNAL Mass Excreted Percent Change from Baseline (%) by Study Product Group and Study Week (PP Population)

Table 14.2.5.1.1.3.2 Summary of Urinary NNAL Mass Excreted Percent Change from Baseline (%) by Study Product Group and Study Week (ITT Population)

Table 14.2.5.1.1.4.1 Summary of Urinary NNAL Creatinine-Normalized Excretion Level (unit) by Study Product Group and Study Week (PP Population)

Table 14.2.5.1.1.4.2 Summary of Urinary NNAL Creatinine-Normalized Excretion Level (unit) by Study Product Group and Study Week (ITT Population)

Table 14.2.5.1.1.5.1 Summary of Urinary NNAL Creatinine-Normalized Excretion Level Change from Baseline (unit) by Study Product Group and Study Week (PP Population)

Table 14.2.5.1.1.5.2 Summary of Urinary NNAL Creatinine-Normalized Excretion Level Change from Baseline (unit) by Study Product Group and Study Week (ITT Population)

Table 14.2.5.1.1.6.1 Summary of Urinary NNAL Creatinine-Normalized Excretion Level Percent Change from Baseline (%) by Study Product Group and Study Week (PP Population)

Table 14.2.5.1.1.6.2 Summary of Urinary NNAL Creatinine-Normalized Excretion Level Percent Change from Baseline (%) by Study Product Group and Study Week (ITT Population)

Table 14.2.5.1.2 Statistical Comparison of Urinary NNAL Mass Excreted (unit) at Weeks 2 and 6 Versus Week -1 by Study Product Group (PP Population)

Table 14.2.5.1.3 Statistical Comparison of Urinary NNAL Mass Excreted (unit) Among Study Product Groups at Weeks 2 and 6 (PP Population)

Urine NNN

Table 14.2.5.2.1.1.1 Summary of Urinary NNN Mass Excreted (unit) by Study Product Group and Study Week (PP Population)

Table 14.2.5.2.1.1.2 Summary of Urinary NNN Mass Excreted (unit) by Study Product Group and Study Week (ITT Population)

Table 14.2.5.2.1.2.1 Summary of Urinary NNN Mass Excreted Change from Baseline (unit) by Study Product Group and Study Week (PP Population)

Table 14.2.5.2.1.2.2 Summary of Urinary NNN Mass Excreted Change from Baseline (unit) by Study Product Group and Study Week (ITT Population)

Table 14.2.5.2.1.3.1 Summary of Urinary NNN Mass Excreted Percent Change from Baseline (%) by Study Product Group and Study Week (PP Population)

Table 14.2.5.2.1.3.2 Summary of Urinary NNN Mass Excreted Percent Change from Baseline (%) by Study Product Group and Study Week (ITT Population)

Table 14.2.5.2.1.4.1 Summary of Urinary NNN Creatinine-Normalized Excretion Level (unit) by Study Product Group and Study Week (PP Population)

Table 14.2.5.2.1.4.2 Summary of Urinary NNN Creatinine-Normalized Excretion Level (unit) by Study Product Group and Study Week (ITT Population)

Table 14.2.5.2.1.5.1 Summary of Urinary NNN Creatinine-Normalized Excretion Level Change from Baseline (unit) by Study Product Group and Study Week (PP Population)

Table 14.2.5.2.1.5.2 Summary of Urinary NNN Creatinine-Normalized Excretion Level Change from Baseline (unit) by Study Product Group and Study Week (ITT Population)

Table 14.2.5.2.1.6.1 Summary of Urinary NNN Creatinine-Normalized Excretion Level Percent Change from Baseline (%) by Study Product Group and Study Week (PP Population)

Table 14.2.5.2.1.6.2 Summary of Urinary NNN Creatinine-Normalized Excretion Level Percent Change from Baseline (%) by Study Product Group and Study Week (PP Population)

Table 14.2.5.2.2 Statistical Comparison of Urinary NNN Mass Excreted (unit) at Weeks 2 and 6 Versus Week -1 by Study Product Group (PP Population)

Table 14.2.5.2.3 Statistical Comparison of Urinary NNN Mass Excreted (unit) Among Study Product Groups at Weeks 2 and 6 (PP Population)

Urine 3-HPMA

Table 14.2.5.3.1.1.1 Summary of Urinary 3-HPMA Mass Excreted (unit) by Study Product Group and Study Week (PP Population)

Table 14.2.5.3.1.1.2 Summary of Urinary 3-HPMA Mass Excreted (unit) by Study Product Group and Study Week (ITT Population)

Table 14.2.5.3.1.2.1 Summary of Urinary 3-HPMA Mass Excreted Change from Baseline (unit) by Study Product Group and Study Week (PP Population)

Table 14.2.5.3.1.2.2 Summary of Urinary 3-HPMA Mass Excreted Change from Baseline (unit) by Study Product Group and Study Week (ITT Population)

Table 14.2.5.3.1.3.1 Summary of Urinary 3-HPMA Mass Excreted Percent Change from Baseline (%) by Study Product Group and Study Week (PP Population)

Table 14.2.5.3.1.3.2 Summary of Urinary 3-HPMA Mass Excreted Percent Change from Baseline (%) by Study Product Group and Study Week (ITT Population)

Table 14.2.5.3.1.4.1 Summary of Urinary 3-HPMA Creatinine-Normalized Excretion Level (unit) by Study Product Group and Study Week (PP Population)

Table 14.2.5.3.1.4.2 Summary of Urinary 3-HPMA Creatinine-Normalized Excretion Level (unit) by Study Product Group and Study Week (ITT Population)

Table 14.2.5.3.1.5.1 Summary of Urinary 3-HPMA Creatinine-Normalized Excretion Level Change from Baseline (unit) by Study Product Group and Study Week (PP Population)

Table 14.2.5.3.1.5.2 Summary of Urinary 3-HPMA Creatinine-Normalized Excretion Level Change from Baseline (unit) by Study Product Group and Study Week (ITT Population)

Table 14.2.5.3.1.6.1 Summary of Urinary 3-HPMA Creatinine-Normalized Excretion Level Percent Change from Baseline (%) by Study Product Group and Study Week (PP Population)

Table 14.2.5.3.1.6.2 Summary of Urinary 3-HPMA Creatinine-Normalized Excretion Level Percent Change from Baseline (%) by Study Product Group and Study Week (ITT Population)

Table 14.2.5.3.2 Statistical Comparison of Urinary 3-HPMA Mass Excreted (unit) at Weeks 2 and 6 Versus Week -1 by Study Product Group (PP Population)

Table 14.2.5.3.3 Statistical Comparison of Urinary 3-HPMA Mass Excreted (unit) Among Study Product Groups at Weeks 2 and 6 (PP Population)

Urine S-PMA

Table 14.2.5.4.1.1.1 Summary of Urinary S-PMA Mass Excreted (unit) by Study Product Group and Study Week (PP Population)

Table 14.2.5.4.1.1.2 Summary of Urinary S-PMA Mass Excreted (unit) by Study Product Group and Study Week (ITT Population)

Table 14.2.5.4.1.2.1 Summary of Urinary S-PMA Mass Excreted Change from Baseline (unit) by Study Product Group and Study Week (PP Population)

Table 14.2.5.4.1.2.2 Summary of Urinary S-PMA Mass Excreted Change from Baseline (unit) by Study Product Group and Study Week (ITT Population)

Table 14.2.5.4.1.3.1 Summary of Urinary S-PMA Mass Excreted Percent Change from Baseline (%) by Study Product Group and Study Week (PP Population)

Table 14.2.5.4.1.3.2 Summary of Urinary S-PMA Mass Excreted Percent Change from Baseline (%) by Study Product Group and Study Week (ITT Population)

Table 14.2.5.4.1.4.1 Summary of Urinary S-PMA Creatinine-Normalized Excretion Level (unit) by Study Product Group and Study Week (PP Population)

Table 14.2.5.4.1.4.2 Summary of Urinary S-PMA Creatinine-Normalized Excretion Level (unit) by Study Product Group and Study Week (ITT Population)

Table 14.2.5.4.1.5.1 Summary of Urinary S-PMA Creatinine-Normalized Excretion Level Change from Baseline (unit) by Study Product Group and Study Week (PP Population)

Table 14.2.5.4.1.5.2 Summary of Urinary S-PMA Creatinine-Normalized Excretion Level Change from Baseline (unit) by Study Product Group and Study Week (ITT Population)

Table 14.2.5.4.1.6.1 Summary of Urinary S-PMA Creatinine-Normalized Excretion Level Percent Change from Baseline (%) by Study Product Group and Study Week (PP Population)

Table 14.2.5.4.1.6.2 Summary of Urinary S-PMA Creatinine-Normalized Excretion Level Percent Change from Baseline (%) by Study Product Group and Study Week (ITT Population)

Table 14.2.5.4.2 Statistical Comparison of Urinary S-PMA Mass Excreted (unit) at Weeks 2 and 6 Versus Week -1 by Study Product Group (PP Population)

Table 14.2.5.4.3 Statistical Comparison of Urinary S-PMA Mass Excreted (unit) Among Study Product Groups at Weeks 2 and 6 (PP Population)

Urine 1-OHP

Table 14.2.5.5.1.1.1 Summary of Urinary 1-OHP Mass Excreted (unit) by Study Product Group and Study Week (PP Population)

Table 14.2.5.5.1.1.2 Summary of Urinary 1-OHP Mass Excreted (unit) by Study Product Group and Study Week (ITT Population)

Table 14.2.5.5.1.2.1 Summary of Urinary 1-OHP Mass Excreted Change from Baseline (unit) by Study Product Group and Study Week (PP Population)

Table 14.2.5.5.1.2.2 Summary of Urinary 1-OHP Mass Excreted Change from Baseline (unit) by Study Product Group and Study Week (ITT Population)

Table 14.2.5.5.1.3.1 Summary of Urinary 1-OHP Mass Excreted Percent Change from Baseline (%) by Study Product Group and Study Week (PP Population)

Table 14.2.5.5.1.3.2 Summary of Urinary 1-OHP Mass Excreted Percent Change from Baseline (%) by Study Product Group and Study Week (ITT Population)

Table 14.2.5.5.1.4.1 Summary of Urinary 1-OHP Creatinine-Normalized Excretion Level (unit) by Study Product Group and Study Week (PP Population)

Table 14.2.5.5.1.4.2 Summary of Urinary 1-OHP Creatinine-Normalized Excretion Level (unit) by Study Product Group and Study Week (ITT Population)

Table 14.2.5.5.1.5.1 Summary of Urinary 1-OHP Creatinine-Normalized Excretion Level Change from Baseline (unit) by Study Product Group and Study Week (PP Population)

Table 14.2.5.5.1.5.2 Summary of Urinary 1-OHP Creatinine-Normalized Excretion Level Change from Baseline (unit) by Study Product Group and Study Week (ITT Population)

Table 14.2.5.5.1.6.1 Summary of Urinary 1-OHP Creatinine-Normalized Excretion Level Percent Change from Baseline (%) by Study Product Group and Study Week (PP Population)

Table 14.2.5.5.1.6.2 Summary of Urinary 1-OHP Creatinine-Normalized Excretion Level Percent Change from Baseline (%) by Study Product Group and Study Week (ITT Population)

Table 14.2.5.5.2 Statistical Comparison of Urinary 1-OHP Mass Excreted (unit) at Weeks 2 and 6 Versus Week -1 by Study Product Group (PP Population)

Table 14.2.5.5.3 Statistical Comparison of Urinary 1-OHP Mass Excreted (unit) Among Study Product Groups at Weeks 2 and 6 (PP Population)

Urine Tneq

Table 14.2.5.6.1.1.1 Summary of Urinary Tneq Mass Excreted (unit) by Study Product Group and Study Week (PP Population)

Table 14.2.5.6.1.1.2 Summary of Urinary Tneq Mass Excreted (unit) by Study Product Group and Study Week (ITT Population)

Table 14.2.5.6.1.2.1 Summary of Urinary Tneq Mass Excreted Change from Baseline (unit) by Study Product Group and Study Week (PP Population)

Table 14.2.5.6.1.2.2 Summary of Urinary Tneq Mass Excreted Change from Baseline (unit) by Study Product Group and Study Week (ITT Population)

Table 14.2.5.6.1.3.1 Summary of Urinary Tneq Mass Excreted Percent Change from Baseline (%) by Study Product Group and Study Week (PP Population)

Table 14.2.5.6.1.3.2 Summary of Urinary Tneq Mass Excreted Percent Change from Baseline (%) by Study Product Group and Study Week (ITT Population)

Table 14.2.5.6.1.4.1 Summary of Urinary Tneq Creatinine-Normalized Excretion Level (unit) by Study Product Group and Study Week (PP Population)

Table 14.2.5.6.1.4.2 Summary of Urinary Tneq Creatinine-Normalized Excretion Level (unit) by Study Product Group and Study Week (ITT Population)

Table 14.2.5.6.1.5.1 Summary of Urinary Tneq Creatinine-Normalized Excretion Level Change from Baseline (unit) by Study Product Group and Study Week (PP Population)

Table 14.2.5.6.1.5.2 Summary of Urinary Tneq Creatinine-Normalized Excretion Level Change from Baseline (unit) by Study Product Group and Study Week (ITT Population)

Table 14.2.5.6.1.6.1 Summary of Urinary Tneq Creatinine-Normalized Excretion Level Percent Change from Baseline (%) by Study Product Group and Study Week (PP Population)

Table 14.2.5.6.1.6.2 Summary of Urinary Tneq Creatinine-Normalized Excretion Level Percent Change from Baseline (%) by Study Product Group and Study Week (ITT Population)

Table 14.2.5.6.2 Statistical Comparison of Urinary 3-HPMA Mass Excreted (unit) at Weeks 2 and 6 Versus Week -1 by Study Product Group (PP Population)

Table 14.2.5.6.3 Statistical Comparison of Urinary Tneq Mass Excreted (unit) Among Study Product Groups at Weeks 2 and 6 (PP Population)

Blood COHb

Table 14.2.5.7.1.1.1 Summary of Blood COHb (unit) by Study Product Group and Study Week (PP Population)

Table 14.2.5.7.1.1.2 Summary of Blood COHb (unit) by Study Product Group and Study Week (ITT Population)

Table 14.2.5.7.1.2.1 Summary of Blood COHb Change from Baseline (unit) by Study Product Group and Study Week (PP Population)

Table 14.2.5.7.1.2.2 Summary of Blood COHb Change from Baseline (unit) by Study Product Group and Study Week (ITT Population)

Table 14.2.5.7.1.3.1 Summary of Blood COHb Percent Change from Baseline (%) by Study Product Group and Study Week (PP Population)

Table 14.2.5.7.1.3.2 Summary of Blood COHb Percent Change from Baseline (%) by Study Product Group and Study Week (ITT Population)

Table 14.2.5.7.2 Statistical Comparison of Blood COHb (unit) at Weeks 2 and 6 Versus Week -1 by Study Product Group (PP Population)

Table 14.2.5.7.3 Statistical Comparison of Blood COHb (unit) Among Study Product Groups at Weeks 2 and 6 (PP Population)

